6 ANALYSIS SEQUENCE

6.1 Interim analysis

Prior to the completion of the study, an interim analysis with a cut-off dated 08-May-2018 will be performed in case the study was not completed up to that date. The results will be presented at the ASCO annual meeting 2018. The results will include patient characteristics in the different analysis populations. Primary and secondary biomarker analyses of the samples available up to that date and safety analyses.

6.2 Final analysis

The final analysis will report all the analyses planned for the study.

7 STATISTICAL METHODS

7.1 General considerations

The demographic and baseline numeric variables will be summarized by the number of patients, the number of valid patients, mean, standard deviation, median, quartiles, maximum and minimum. The frequency and percentages based on the total of patients in the analysis set will be reported for the categorical variables. Quantitative variables will be summarized by the number of patients, mean, median, 95% confidence interval, standard deviation, quartiles, minimum and maximum, as appropriate. Qualitative variables will be summarized by the frequency, the percentage and the confidence interval of the odds ratio, where appropriate.

Time-to-event variables will be summarized by showing the number of events, percentage, median survival with its 95% confidence interval, and will be analyzed through the Kaplan-Meyer method.

The evolution of quantitative variables will be analyzed through the Wilcoxon's non-parametric test, mean difference, medians and their 95% confidence intervals.

The evolution of qualitative variables will be analyzed through the McNemar test.

No inferential statistics will be performed for baseline variables or safety variables, unless otherwise specified.

7.2 Populations for analysis

(ICH E3; 9.7.1, 11.4.2.5. ICH E9; 5.2)

Full analysis set

This set will include all the patients who have received the treatment. This set will also be the safety analysis set.

Per protocol set

This set will include all the patients of the full analysis set that do not have major protocol violations that may affect the assessment of treatment in the primary variable (e.g., non-evaluable patients for

biomarkers). The definition of these deviations is described in section 9.1. For the analysis of secondary variables, the number of evaluable patients for a certain biomarker analysis set will be considered.

Sensitivity analysis

The primary biomarker analysis (significant inhibition of cyclin D1, Ki67 and active caspase-3) and the secondary analyses will be performed in the full analysis set and the per protocol population.

The safety analyses will be performed in the full analysis set.

PKD population

We propose to analyze and model pharmacokinetics (PK), pharmacokinetics-pharmacodynamic (PBMC) and AZD2281 concentration, considering all patients with a complete treatment concentration-time profile.

Analyses will not be repeated between different analysis populations if they only differ by 10% patients. The largest analysis population will be used for the analyses.

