5.4 Sample size calculation

(ICH E3; 9.7.2. ICH E9; 3.5)

The primary objective is to identify, in human tumor samples, biomarker changes associated with short exposure to AZD2281 as potential predictors of activity in Endometrial Carcinoma (EC). The primary endpoint is the difference between pre and post treatment immunostaining of cyclin D1, Ki67 and active caspase 3 on endometrial tumor tissue, after four weeks of treatment. Therefore, the primary analysis will be based on comparing pre and post treatment immunostaining on target biomarkers. The histological

score will be obtained by applying the following formula: $Hscore = 1x(\%light staining) + 2x(\%moderate staining) + 3x(\%strong staining)$. Although a preliminary power analysis has been performed, in agreement with the exploratory nature of phase 0 studies, the sample size has been limited to 36 patients (It is expected that each participating site includes an average of about 6-10 patients) for clinical and practical considerations, rather than statistical ones (Kummar et al 2009).

Analysis will be performed in accordance with a statistical evaluation scheme specifically developed for Phase 0 trials (Rubinstein et al 2010). In the analysis we will define response at the patient level (patients with significant inhibition of biomarkers), before analyzing the number of responding patients in the study sample.

Definition of response at the patient level:

Significant inhibition of biomarker activity is defined as the reduction in biomarker levels after four weeks treatment exposure (compared to baseline) that should satisfy two criteria: reduction is at least 50 % (biological), and reduction is sufficient when compared to the variation among the baseline values, to yield 95 % statistical confidence that it is not due to chance variations.

Variability will be measured on log-transformed values. The standard deviation (SD) will be the square root of baseline inter-patient variance. Pre- and post-treatment difference of log PIK1 values will be compared to the threshold of 1.6448 SD (normal distribution is used because number of samples is higher than 30), to establish statistically significant reduction at the one-sided 0.05 level.

Definition of a significant effect at study sample:

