7.3 Covariate and subset analysis

(ICH E3; 9.7.1, 11.4.2.1. ICH E9; 5.7. CPMP 2002; 4. CPMP 2003.)

In the covariate and subset analysis, the pre-treatment and post-treatment biomarker levels and the differences between these two periods will be analyzed. For the subset analysis, biomarker levels will be compared through the Mann-Whitney U test. When comparing qualitative variables between different subsets, the Chi-square test or Fisher's exact test will be used. The correlation between different quantitative variables or discrete variables will be performed through Spearman's correlation, and their corresponding 95% confidence intervals will be presented. The subset analysis will include the difference of the biomarker level depending on the different molecular (p53, MSI, POLE...) and clinical (days since surgery, administration breach [>3 days, >6 days, ≥ 14 days]) classifications.

[figure not shown]

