7.4 Pharmacokinetic analysis

Plasma samples for pharmacokinetic evaluation will be analyzed for each patient on days 1 (before first dose of olaparib and 1 to 4 hours after the first dose), day 7 (1 to 4 hours after olaparib dose), day 14 (1 to 4 hours after olaparib dose), day 21 (1 to 4 hours after olaparib dose), the last day of treatment (1 to 4 hours after olaparib dose) and the day of surgery (preferably 1 to 4 hours before, or within 24h prior to surgery).

All samples will be analyzed to determine olaparib level and the plasma concentration versus time data, together with information about dosing and patient characteristics will be pooled and analyzed using a population pharmacokinetic analysis approach to obtain *post-hoc* estimates of steady-state area under the concentration-time curve of AZD2281.

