7.5 Pharmacokinetic-pharmacodynamic modeling (PBMC modeling)

The pharmacokinetic-pharmacodynamic modeling, in which the variable of time is incorporated into the relationship of drug effect and both plasma and tissue concentration will be described.

As a model PK/PD the relationship established between PARP inhibition in patient PBMCs after administration of olaparib, expressed as a mean percentage of PARP activity before administration of olaparib over time vs. plasma exposure using a simple E_{max} model, will be used.

The estimate of the existing correlation between mean plasma levels and the differences from baseline activity in PARP, HIF1, GLUT1 and CICLIND1 activity will be performed. MS1 levels will be dismissed because there is no drug, MS2 levels, because C_{max} is reached after the first dose, and MS7 levels, because of the end of treatment. This same analysis will look for the correlation between the levels and the final activity of biomarkers. Based on the time-concentration curve, the existing correlation between drug exposure and biomarker activity will be estimated.

Finally, mean plasma levels and mean exposure between the sets of patients with and without significant biomarker inhibition will be compared. The definition of the response level defined in the protocol (page 11/20 section Definition of the Response Level) will be applied here.

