7.6 Missing data imputation

(ICH E3; 9.7.1, 11.4.2.2. ICH E9; 5.3. EMA Guideline on Missing Data in Confirmatory Clinical Trials)

Patients without quantitative biomarker values at the baseline visit will be assigned the mean of the patients at that visit. Patients without quantitative values at the follow-up visits will be assigned the same value as in the baseline visit. This imputation is intended to be conservative and go against the study objective (to detect a significant evolution between pre- and post-treatment biomarker values). In the case of qualitative variables, the lack of mutation or the characteristic analyzed will be assumed.

The different study populations where the different analyses will be performed will help to assess the imputation on the results. The analyses are only considered positive if the result is equivalent in all the analysis populations used.

7.7 Analysis of the specific effects of each site.

(ICH E3; 9.7.1, 11.4.2.4. ICH E9; 3.2)

The number of patients enrolled in each site will be described. Considering the small sample size, no analyses are expected to adjust the results by the site effect.

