8 PROTOCOL DEVIATIONS

Description	Category	Does the deviation exclude the analysis population?			
		Full analysis and safety set	Per protocol set	Biomarker analysis subset	PKD population
Unsigned Informed Consent (main and sample).	Inclusion/Exclusion	Yes	Yes	Yes	Yes
Signed an outdated version.	Inclusion/Exclusion	Case by case	Case by case	Case by case	Case by case
The investigational product was not provided.	Treatment	Yes	Yes	Yes	Yes
Treatment was discontinued early, but the patient has received at least one administration.	Treatment.	No	Case by case	Case by case	Case by case
Patients with missing or non-evaluable pre-treatment and post-treatment biomarker/PK values.	Biomarker analysis	No	Case by case	Case by case	Yes
Patients who do not have type I primary endometrial carcinoma (EC) (see	Inclusion/Exclusion	No	Case by case	Case by case	Case by case

UICC-FIGO Classification [Stage]).						
Age < 18 years.		Inclusion/Exclusion	No	Case by case	No	No
ECOG>2.		Inclusion/Exclusion	No	No	No	No
Inappropriate organic function: ANC < 1.5 x 10 ⁹ /L Platelets < 100 x 10 ⁹ /L Hb ≤ 10g/dL Serum bilirubin > 1.5 x ULN INR ≥ 1.3 (o ≥ 3) ALT and AST > 2.5 x ULN Serum creatinine > 1.5 x mg/dL Serum cholesterol > 300 mg/dL or > 7.75 mmol/L Triglycerides > 2.5 x ULN		Inclusion/Exclusion	No	No	No	Case by case (PK-PD Modeling)
Prior anti-cancer treatments for current endometrial cancer.		Inclusion/Exclusion	No	Case by case	Case by case	Case by case
Major surgery or significant injury within the four weeks prior to start of the study drug.		Inclusion/Exclusion	No	Case by case	No	No
Side effects of any major surgery or major surgery throughout the study.		Inclusion/Exclusion	No	No	No	No
Serious and/or uncontrolled condition.		Inclusion/Exclusion	No	Case by case	Case by case	Case by case
Prior prohibited medication		Inclusion/Exclusion	No	Case by case	Case by case	Case by case
Pregnant or nursing (lactating) women.		Inclusion/Exclusion	No	No	No	No
Urine or serum pregnancy		Inclusion/Exclusion	No	No	No	No

test with positive result within 7 days before first dose administration.						
History of non-compliance with medical regimens.	Inclusion/Exclusion	No	Case by case	Case by case	Case by case	Case by case
Patients unwilling to or unable to comply with the protocol.	Inclusion/Exclusion	No	Case by case	Case by case	Case by case	Case by case

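### SAP 7.2 restricts PK and PK-PD work to 'complete' profiles that the methods in 7.4 and 7.5 do not need, and 7.5 names only one of the three primary markers for plasma level against change

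*SAP*

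**What the plan says.** **Population.** SAP 7.2 sets the PKD population by "considering all patients with a complete treatment concentration-time profile". It gives no number of samples, days or time windows.

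**Section 8.** Two rows of the deviation table bear on the PKD column. The row "Patients with missing or non-evaluable pre-treatment and post-treatment biomarker/PK values" is marked as excluding. The row for some of MS2 to MS7 missing or taken off time is marked case by case.

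**PK method.** SAP 7.4 schedules seven plasma samples: before and after the first dose on day 1, days 7, 14 and 21, the last treatment day, and the day of surgery. All are assayed, and the data "together with information about dosing and patient characteristics will be pooled and analyzed using a population pharmacokinetic analysis approach" to give post-hoc steady-state AUC.

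**PK-PD.** SAP 7.5 leaves MS1, MS2 and MS7 out of the mean plasma level. It plans a correlation of that level with "differences from baseline activity in PARP, HIF1, GLUT1 and CICLIND1 activity will be performed". It then adds: "This same analysis will look for the correlation between the levels and the final activity of biomarkers". Another sentence relates exposure to biomarker activity in general. The section closes by comparing plasma level and exposure between patients with and without significant inhibition.

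**Primary markers.** SAP 5.4 states: "The primary endpoint is the difference between pre and post treatment immunostaining of cyclin D1, Ki67 and active caspase 3".

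**The concern.** The study has no control group, and the SAP introduction gives phase 0 work the purpose of supporting a go or no-go decision. A weak biomarker change could mean that the drug has no effect or that too little drug was present. The exposure analyses are the part of the plan that helps to tell these apart, and with at most 36 patients they cannot spare many.

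Two features weaken them.

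- The entry condition for the PKD population is stricter than the analysis needs, and it is undefined. Two analysts could build different populations from the same data, after seeing them, in an open-label study.
- For Ki67 and active caspase 3, the most direct exposure analysis, plasma level against change from baseline, is not named.

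**Working it through.** The documents give no sample size, power or precision for the PK-PD analyses, so there is no stated figure to reproduce.

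**Step 1. Samples required against samples used.** Following the order in 7.4, MS1 and MS2 are the two day-1 samples, MS3 to MS5 are days 7, 14 and 21, MS6 is the last treatment day and MS7 the day of surgery. A complete profile, read strictly, needs 7 samples. The mean level in 7.5 uses 7 − 3 = 4 (MS3 to MS6). The population PK model in 7.4 needs no fixed number per patient.

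**Step 2. What section 8 settles.** The two rows may separate total loss (excluded) from partial loss (case by case). The table does not say so, and neither row defines completeness.

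**Step 3. Patients kept under different rules.** Inputs: N = 36 (SAP 5.4); capture probability c per sample, independent between samples. The documents give no c, so it is an assumption, shown over a range.

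- Rule needing all k samples: expected N = 36 × c^k
- Rule needing at least one of MS3–MS6: expected N = 36 × [1 − (1 − c)^4]

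| Assumed c | All 7 | The 4 used in 7.5 | At least 1 of those 4 |
|---|---|---|---|
| 99% | 33.6 | 34.6 | 36.0 |
| 95% | 25.1 | 29.3 | 36.0 |
| 90% | 17.2 | 23.6 | 36.0 |
| 85% | 11.5 | 18.8 | 36.0 |

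For example, 0.95^7 = 0.698 and 36 × 0.698 = 25.1; 0.90^4 = 0.656 and 36 × 0.656 = 23.6.

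**Step 4. Precision.** The approximate 95% interval for an observed correlation of 0.4 is tanh(atanh(0.4) ± 1.96/√(n − 3)):

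- n = 36: 0.08 to 0.64
- n = 25: 0.01 to 0.69
- n = 17: −0.10 to 0.74

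**Step 5. Power.** Simulated bivariate normal data, Spearman test (the SAP 7.3 method), assumed true correlation 0.4, patients lost at random:

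| Two-sided level | 36 patients | 4 lost (n = 32) |
|---|---|---|
| 10% | 75% | 70% |
| 5% | 64% | 58% |
| 1% | 39% | 33% |

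At 5%, power is 61% with 2 lost and 55% with 6 lost. For a true correlation of 0.5 it falls from 85% to 80% with 4 lost. Other levels are shown because SAP 7.8 judges secondary tests by a 10% false discovery rate, not a fixed level.

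**Step 6. Markers, side by side.**

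| Marker | Primary (5.4) | Named in 7.5 for level against change |
|---|---|---|
| Cyclin D1 | yes | yes |
| Ki67 | yes | no |
| Active caspase 3 | yes | no |
| PARP, HIF1, GLUT1 | no | yes |

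One of three primary markers is named. GLUT1 is named although no objective or endpoint in either document lists it.

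**The case against.** **Partial loss need not exclude anyone.** If the two section 8 rows mean total against partial loss, a missing sample never forces exclusion, and 7.4 assays and pools all samples. SAP 7.2 also says that analyses are not repeated where populations differ by only 10%, and that the largest is then used. If this covers the PKD population, losing up to 3 of 36 (8.3%) changes nothing, while 4 of 36 (11.1%) passes the limit. This stands as a possible reading. It would be safer to write it down than to rely on it.

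**Dosing breaks need not remove the low-exposure end.** A reader might infer that patients with long breaks have incomplete profiles, drop out, and take the lowest exposures with them. Simulated power would then fall from 64% to 45% with 4 lost. The documents do not support this. The SAP's exposure measures are levels drawn 1 to 4 hours after a dose and post-hoc steady-state AUC, and a break does not make a patient lowest on either. Keeping such patients may even dilute the correlation. If 4 of them have average measured levels but a change weaker by an assumed 0 to 1.5 SD, power is 64% down to 55% with them in, against 58% without them. Near-random loss is the fair figure.

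**The marker list follows the objective.** SAP 4.1 bases PK-PD on plasma concentration and tissue PARP inhibition. That explains why PARP comes first. It does not explain a list that already extends to HIF1, GLUT1 and cyclin D1 but leaves out two primary markers.

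**Other sentences may cover Ki67 and active caspase 3.** A reader might infer that these markers are absent from all PK-PD work. That goes too far. The responder comparison at the end of 7.5 rests on a pre-to-post reduction and can include them, but only as responder against non-responder. The sentences on final activity and exposure, and the general Spearman sentence in 7.3, may also reach them. None states plasma level against change for these two markers.

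**Conclusion.** The point holds as a minor, cheap improvement to a secondary objective.

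- The restriction to complete profiles is undefined and is not needed by the methods it governs. Read strictly, it can exclude a patient for a sample that the mean-level analysis discards.
- The possible cost depends on capture rates that the documents do not give. Under assumed independent capture of 95% or 90%, about 25 or 17 of 36 patients remain if all seven samples are required, and about 29 or 24 if the four used samples are required. A loss of 4 at random costs about 6 percentage points of power (64% to 58%) for an assumed correlation of 0.4.
- A larger power loss for the same number dropped would need those patients to be lowest on the SAP's own exposure measures, which the documents do not show.
- The marker gap is limited to the continuous correlation of plasma level with change from baseline.

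Nothing here touches the primary rule of 5 of 36, which uses no PK data.

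**What to change.** 1. **Population.** For population PK, include every treated patient with a dosing record and at least one evaluable post-dose sample. For the 7.5 mean-level correlations, require at least one evaluable sample from MS3 to MS6; a patient with only MS2 or MS7 has no mean level as 7.5 defines it. Align the two section 8 rows with these rules, and report the number of samples per patient.
2. **Markers.** Add Ki67 and active caspase 3 to the 7.5 correlation with change from baseline, in patients with both tissue samples. The tissue condition is needed because of SAP 7.6: "Patients without quantitative values at the follow-up visits will be assigned the same value as in the baseline visit". An imputed change of zero would otherwise enter the correlation as if it had been observed.

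**Cost.** SAP wording only, with no new samples. It adds two tests to the 10% false discovery rate family, and post-hoc PK estimates are less precise for patients with few samples; the sample counts make that visible.

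**Optional.** A correlation of dose taken over dose planned with marker change could sit beside the dosing-breach classes in 7.3. It may be confounded by toxicity and is not part of the required change.

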7.3 Covariate and subset analysis

(ICH E3; 9.7.1, 11.4.2.1. ICH E9; 5.7. CPMP 2002; 4. CPMP 2003.)

In the covariate and subset analysis, the pre-treatment and post-treatment biomarker levels and the differences between these two periods will be analyzed. For the subset analysis, biomarker levels will be compared through the Mann-Whitney U test. When comparing qualitative variables between different subsets, the Chi-square test or Fisher's exact test will be used. The correlation between different quantitative variables or discrete variables will be performed through Spearman's correlation, and their corresponding 95% confidence intervals will be presented. The subset analysis will include the difference of the biomarker level depending on the different molecular (p53, MSI, POLE...) and clinical (days since surgery, administration breach [>3 days, >6 days, ≥ 14 days]) classifications.

[figure not shown]
7.4 Pharmacokinetic analysis

Plasma samples for pharmacokinetic evaluation will be analyzed for each patient on days 1 (before first dose of olaparib and 1 to 4 hours after the first dose), day 7 (1 to 4 hours after olaparib dose), day 14 (1 to 4 hours after olaparib dose), day 21 (1 to 4 hours after olaparib dose), the last day of treatment (1 to 4 hours after olaparib dose) and the day of surgery (preferably 1 to 4 hours before, or within 24h prior to surgery).

All samples will be analyzed to determine olaparib level and the plasma concentration versus time data, together with information about dosing and patient characteristics will be pooled and analyzed using a population pharmacokinetic analysis approach to obtain *post-hoc* estimates of steady-state area under the concentration-time curve of AZD2281.

7.5 Pharmacokinetic-pharmacodynamic modeling (PBMC modeling)

The pharmacokinetic-pharmacodynamic modeling, in which the variable of time is incorporated into the relationship of drug effect and both plasma and tissue concentration will be described.

As a model PK/PD the relationship established between PARP inhibition in patient PBMCs after administration of olaparib, expressed as a mean percentage of PARP activity before administration of olaparib over time vs. plasma exposure using a simple E_{max} model, will be used.

The estimate of the existing correlation between mean plasma levels and the differences from baseline activity in PARP, HIF1, GLUT1 and CICLIND1 activity will be performed. MS1 levels will be dismissed because there is no drug, MS2 levels, because C_{max} is reached after the first dose, and MS7 levels, because of the end of treatment. This same analysis will look for the correlation between the levels and the final activity of biomarkers. Based on the time-concentration curve, the existing correlation between drug exposure and biomarker activity will be estimated.

Finally, mean plasma levels and mean exposure between the sets of patients with and without significant biomarker inhibition will be compared. The definition of the response level defined in the protocol (page 11/20 section Definition of the Response Level) will be applied here.

